3.6.3. Laboratory specimen collection, transport and analysis – serological test

A biological sample/specimen for serological testing will be collected at each of the 5 testing periods.

Biological sample collection for serological testing will be conducted by 5 teams of 2 nurses (3 teams for the NL schools and 2 teams for the FR schools). If a saliva swab will be suitable for this study (see information below) self-sampling, under the supervision of the nurse, will be performed. The self-sampling will be done in groups of 5 to 10 pupils and can be done outside. Half a day will be needed to sample the students and staff in one school. The sample material for the three sampling periods as well as labelling stickers will be provided by Sciensano.

Sample type

Since sampling must be done repeatedly in children, a non-invasive sampling method, such as antibody determination in saliva samples, would help to recruit children and keep them in the study for seven months. Therefore, the saliva test, (Oracol or equivalent) (Malvern Medical Developments, UK) has been chosen for this study. The saliva sample method for detection of immunoglobulins in SARS-CoV-2 has been validated in the adult population by Sciensano in a Belgian healthcare workers study (18). Oracol has been validated in the paediatric population for other infectious diseases (Measles, Dengue)(19). A study is currently been performed in The Netherlands, as part of the PIENTER study, where a proportion of the study participants are children making use of saliva testing, and in the Public Health England Laboratories in the UK (personal communication). Proper validation of saliva samples for SARS-CoV-2 in our target population, remains however necessary, given the still limited and non-published evidence on their performance. For this purpose we will validate antibody testing in saliva samples during a separate study. This study takes place in four selected schools in the province of Limburg. Data from the validation study will be used to define feasibility and accuracy, e.g. but not limited to the sensitivity, specificity. Depending on the validity and accuracy of the salivary samples, the study sample type will be selected. In the unlikely case that the performance of the salivary samples is deemed insufficient, all samples in this study will be collected using capillary blood on dried-blood-spots from the participants. The in this study used assay is validated for capillary blood and multiple countries have validated and successfully used capillary blood in the paediatric population for the collection of antibodies against SARS-CoV-2.

For operational reasons we decided to use the same sample type and procedure for the school staff as the one used for the pupils.

Sample collection

A saliva sample will be collected as per manufacturer and previously in the paediatric population validated instructions. During 1.5 minutes the oral swab will be rubbed with mild pressure against the buccal mucosa of the upper teeth. Samples will be labelled with the study label, data of collection and participant identifier number.

Sample transport

Samples dispatching and collection will be organized by Sciensano using a carrier service. The swaps and biological samples will be delivered and collected at the place of one of the nurses. Collection of

biological samples will be done twice a week. Samples need to be stored at a temperature between 20 and 25°C.

Sample analysis

Analysis of biological samples will be done by Sciensano. A serological test (ELISA) will be conducted on the sample material. The current assay that is used at the laboratory of Sciensano is the Euroimmun (Euroimmun, Medizinische Labordiagnostika, Lübeck, Germany; Cat # EI 2668-9601 G; CE marked March 2020) enzyme-linked immunosorbent assay (ELISA), measuring human antibodies of the class IgG targeting the recombinant S1 domain including the receptor binding domain of the structural protein of SARS-CoV-2. The assay is a medium through-put ELISA requiring in-laboratory testing. The result is read using a microplate reader. As per the manufacturer a ratio is calculated between the optical density (OD) of the patient sample compared to the OD of the calibrator, with a ratio of <0.8 interpreted as negative, between 0.8-1.1 borderline and >1.1: positive, for serum samples. The ELISA test has been validated against the plaque reduction neutralization test (PRNT) (gold standard) by Sciensano. Serum, EDTA plasma and capillary blood (dried blood spot) specimens have been validated by the manufacturer. Accuracy data provided by the manufacturer give a sensitivity of 94.4% (no confidence interval given, n=72, adult samples) and specificity of 100% (in 74 children tested) (<https://www.coronavirus-diagnostics.com/antibody-detection-tests-for-covid-19.html>) using known negative and positive serum samples. Clinical laboratory validation on adult patients showed a specificity of 100%, with 50 out of 50 samples negative (Charlton et al, 2020) Sensitivity using known positive samples showed an overall all point sensitivity of 63% (95% CI 46-77) and of 88% (95%CI 46-100) in patients more than 21 days post PCR confirmed SARS-CoV-2 infection. Overall, combining literature data (Van Elslande et al, 2020) and *in house* validations, a specificity of 98.6% (494/501; 95%CI 97.1-99.3) and a sensitivity of 95.9% (95%CI 88.8-98.9) at ≥ 15 days post onset of symptoms was observed for the Euroimmun IgG Elisa taken a ratio of 1.1 as cut-off (accuracy 98.3% (565/575)). The laboratory technician will have no insight in the participants identifiers and to previous test results. Test results are qualitative and will be reported as presence versus absence of specific antibodies. After analysis, Sciensano will register the results in a separate data sheet. A child identifier database and a non-identifiable database will be kept. Based on the child identifier (unique registration code), child data on the serological test results will be linked with the questionnaire data.

Sample result

Participants and parents/legal caregivers of participating children will be informed about the result of their ~~child's~~ serological test after each sampling period. The schools will receive the individual reports under closed envelopes and distribute them to the primary caregivers of the participating children and the participating staff. Informed consent forms and accompanying letters will clearly state that a positive test result only implies that the child has been in contact with the SARS-CoV-2 virus, but that currently no assumptions can be made on protection against COVID-19 disease, unless new convincing scientific data becomes available about protection against re-infection. A contact number will be given in case questions remain regarding the study sample results. Distribution of test results will be done through Sciensano.

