7.2. POTENTIAL RISKS

- Biological sample (saliva swap) risks are minimal.
- Information of the result can be considered to be psychologically or socially difficult to manage in the current context of a pandemic. The medical staff performing this study will give appropriate advice.

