7.8. DISTRIBUTION OF RESULTS

The study protocol will be registered at [Clinicaltrials.gov](https://clinicaltrials.gov).

Anonymous study results should be made accessible and available as soon as possible after every testing period and at the end of the study to public health authorities involved in management of the COVID-19 epidemic in Belgium. This can be done through a policy brief or presentation. Sciensano will coordinate the distribution of results. These results will be also published on the relevant websites of these institutions.

The general public will also be informed regarding these anonymous results through press communications. This will be done by the communication departments of Sciensano and of the study partners.

Scientific peer-reviewed publications (possible short publication, regular paper) will be prepared to add to the body of evidence and availability for the global scientific community and public health decision makers.

Appendices

a. Questionnaires:

- Parents: 1ste contact,
- Parents: 2nd and 3rd contact,
- Schools: baseline
- Schools: 2nd and 3rd testing period
- Parent registration form
- School staff registration form
- School staff: baseline
- School staff: 2nd and 3rd testing period

b. Additional questions to be added at questionnaire for parents at 4th and 5th testing period

1. Werd uw kind gevaccineerd tegen het coronavirus (COVID-19)?

- Ja, mijn kind kreeg één dosis van een vaccin
- Ja, mijn kind kreeg twee dosissen van een vaccin
- Neen, mijn kind kreeg nog geen vaccin

1.1. Indien optie 1: Datum van de eerste dosis:

1.2. Indien optie 2: Datum van de tweede dosis:

Indien u de exacte datum van de vaccinatie niet kent, kan u aangeven wanneer uw kind ongeveer werd gevaccineerd.

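### The wording prescribed for consent forms and result letters ties a positive test to contact with the virus without allowing for test error, although the protocol's own specificity implies some false positives

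*Combined protocol and SAP*

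**What the plan says.** Section 3.6.3 (Sample result) provides for individual results after every sampling period. It fixes one element of the consent forms and accompanying letters: they are to make clear that "a positive test result only implies that the child has been in contact with the SARS-CoV-2 virus". The second half of that sentence is a warning about immunity: "but that currently no assumptions can be made on protection against COVID-19 disease". A contact number is offered for questions.

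Section 3.6.3 (Sample analysis) describes an ELISA "measuring human antibodies of the class IgG targeting the recombinant S1 domain", with results reported as antibodies present or absent. No confirmatory test is described. Accuracy is given from several sources:
- pooled literature and in-house data, at a cut-off ratio of 1.1 and at least 15 days after symptom onset for sensitivity: "a specificity of 98.6% (494/501; 95%CI 97.1-99.3) and a sensitivity of 95.9% (95%CI 88.8-98.9";
- the manufacturer: "specificity of 100% (in 74 children tested";
- a clinical laboratory series in adults, which "showed a specificity of 100%, with 50 out of 50 samples negative", with sensitivity of 63% overall and 88% beyond 21 days.

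None of these is identified as a saliva figure. Section 3.6.3 (Sample type) leaves saliva accuracy to a separate validation study.

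Sections 3.7 and 6 recognise imperfect test accuracy and deal with it by sensitivity analysis. Section 7.2 lists two risks, and the second is the result itself: "Information of the result can be considered to be psychologically or socially difficult to manage in the current context of a pandemic". Appendix b adds a question on the child's own vaccination for periods 4 and 5: "Werd uw kind gevaccineerd tegen het coronavirus (COVID-19".

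**The concern.** The protocol corrects for test error in its analysis but not in the message it prescribes for participants. At low prevalence, even a specificity near 99% makes a noticeable share of single, unconfirmed positives false. A family following the prescribed sentence would conclude that the child had met the virus, and would have no reason to doubt it.

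What is at stake is the accuracy of what participants are told, both at consent and after each round. Section 7.3 names receiving the result among the benefits and section 7.2 treats it as a possible burden, so its stated meaning matters.

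**Working it through.** **Reproducing the protocol's accuracy figures.** Specificity is 494/501 = 98.6%, and the Wilson 95% interval is 97.1% to 99.3%, as stated. The overall accuracy of 565/575 = 98.3% implies a sensitivity of (565 − 494)/(575 − 501) = 71/74 = 95.9%, also as stated.

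**Inputs.** Sensitivity (Se) 95.9% and specificity (Sp) 98.6% (97.1% to 99.3%) from section 3.6.3; prevalence p = 6% and N = 820 children per age group from section 3.3; prevalence 10% and 820 staff from section 3.4. A prevalence of 20% is my assumption, to show a later and higher level.

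**Formulas.** True positives = N × p × Se. False positives = N × (1 − p) × (1 − Sp). PPV = true positives / all positives.

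**Base case.** True positives: 820 × 0.06 × 0.959 = 47.2. False positives: 820 × 0.94 × 0.014 = 10.8. PPV = 47.2/58.0 = 81.4%, so roughly one positive letter in five would be wrong.

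**Range.**

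| Prevalence | Specificity | True positives | False positives | PPV |
|---|---|---|---|---|
| 6% | 97.1% | 47.2 | 22.4 | 67.9% |
| 6% | 98.6% | 47.2 | 10.8 | 81.4% |
| 6% | 99.3% | 47.2 | 5.4 | 89.7% |
| 6% | 100% | 47.2 | 0 | 100% |
| 10% | 98.6% | 78.6 | 10.3 | 88.4% |
| 20% | 98.6% | 157.3 | 9.2 | 94.5% |

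The 10% row is also the staff case.

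If 6% is read as the observed rather than the true prevalence, true prevalence is (0.06 − 0.014)/(0.959 − 0.014) = 4.9%. PPV is then 0.0487 × 0.959/0.06 = 77.8%.

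**Do the two 100% series rule out 98.6%?** With no false positives among n samples, the exact lower 95% limit is 0.025^(1/n). That is 95.1% for n = 74 and 92.9% for n = 50, so both are compatible with 98.6%.

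**Negatives.** With 49.2 infected children (820 × 0.06), missed infections number 49.2 × 0.041 = 2.0 at 95.9% sensitivity and 49.2 × 0.37 = 18.2 at 63%. The second figure is pessimistic, because the same series gives 88% beyond 21 days.

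**The case against.** The strongest reply is that the sentence has a different purpose. Its second half warns against assuming protection, so *only* is there to stop families inferring immunity. That is a fair reading. The sentence omits test error; it does not claim a perfect test, and a reader who inferred an outright contradiction with the specificity figure would go too far. The omission still matters, because the protocol says this statement must be made clearly and requires nothing to qualify it.

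Second, the letters and consent forms are not in the supplied documents and may contain more. This stands. It cannot be concluded that the forms lack a caveat on negatives, or that consent was in fact inaccurate. The point is confined to the statement the protocol prescribes.

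Third, a reader might infer that participants are misinformed about the risk in section 7.2. They are not: that section names the burden of receiving a result, not the chance of a wrong one. It also promises medical advice, section 3.6.3 offers a contact number, and section 7.3 lets participants decline results. These help but do not correct the statement.

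Fourth, the S1 target invites the inference that vaccinated participants will be told they met the virus. The documents never say that vaccination turns this assay positive, and they give no vaccination rate, so the effect cannot be sized. Periods 4 and 5 involve primary pupils only, and the table of changes expects no licensed vaccine for under-12s when the school year starts. This is a secondary, conditional point.

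Fifth, the figures may not carry over to the remaining rounds. They are not saliva values, and the 6% matches the residual-sample estimate for late April in section 1, whereas periods 4 and 5 fall in late 2021. Higher prevalence would shrink the problem, as the table shows. A reader might also infer a much lower PPV for children who tested negative before: 41%, 68% or 78% if 1%, 3% or 5% were newly infected. Those incidences are assumptions, and the calculation needs false positives to be independent between rounds, which the documents do not establish.

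**Conclusion.** The concern holds as a point about participant information. The prescribed statement makes no allowance for test error, while the protocol's pooled specificity implies about 11 false positives among 58 per round of 820 children at 6% prevalence. That is about one in five, with a range of one in three to one in ten over the specificity interval. The share falls to about 12% at 10% prevalence and 5.5% at 20%, and to zero if specificity is truly 100%.

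This assumes that the pooled figures apply to saliva in children, which only the validation study can show, and that the planning prevalence is the true prevalence. The exact share is therefore uncertain. The need for a caveat is not, since neither 100% series excludes a specificity of 98.6%. No study estimate is affected.

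**What to change.** - Amend the sentence in section 3.6.3 (Sample result), and the letters and forms for periods 4 and 5, to say that a positive suggests past contact with the virus but can be a false positive and, where the child has been vaccinated, may reflect vaccination.
- Add that a negative does not exclude past or recent infection.
- Add the possibility of a false result to section 7.2.

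Giving the approximate chance of a false positive for each round, based on the saliva validation, is optional. So is a separate letter for vaccinated participants.

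The cost is a slightly longer letter and an ethics notification. The extra burden is small because section 7.1 already requires new consent and assent for the extension.

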3.6.4. Practical considerations

Two junior researchers (one Dutch and one French speaking) will be hired for the duration of the study. They will have implementation, coordinating and administrative responsibilities. Research nurses will be recruited for the sampling school-visit periods. It is the responsibility of each team (Flemish and Wallonia) to coach and supervise the junior researcher, to train the nurses (same training content and instructions will be used for Dutch and French speaking nurses) and to prepare the field visits.

Ten research nurses (5 teams of 2 nurses) will be trained for the sampling periods. The aim is to sample 2 schools (2 x 20 pupils) per day, with 8 schools per week per team. Which would take 2 to 3

weeks to sample 82 schools. Preferably the same nurse teams will be recruited for all three sampling periods.

Standard operating procedures (SOPs) for the study implementation (instructions for schools, the school contact person and the research nurses) will be developed and made available. For the research nurses this includes instructions regarding infection and control procedures, based on the most recent and available knowledge to maximally protect both participants and study personnel. Guidelines (federal – regional, e.g. physical distancing, mask use in public etc.) present at the moment of the field work will be respected.

3.6.5. Special considerations and circumstances

- If a school is closed during the planned period of sampling, the sampling will take place as soon as the school reopens. A maximum of 6 weeks after the first school of that sampling period got sampled will be allowed to add the data to the sampling period analysis. On an individual base the case can be made to still collect the data after this 6 week interval, not for inclusion in period data analysis, but to have school based data in relation to the possible outbreak of SARS-CoV-2 virus in this particular school.
- Given the unpredictable future, ad hoc decisions will need to be made when schools in general are closed during the planned sampling period. Postponing the remaining sampling periods will need to be discussed. Alternatively sampling of students on invitations could be considered, if the interest and need for public health is present. The necessary communication and balanced decisions will be made in line with the national guidelines.
- Given the uncertainty about the future development of the COVID-19 epidemic adaptation of sampling periods (more frequent sampling or adding additional sampling period(s) after April/May 2021) and extension of the study **is requested**.

3.7. DATA ANALYSIS

The analysis will be descriptive for the primary objective. Variables will be described as proportions with a 95% Confidence Interval (95%CI). Several epidemiological parameters/effect measures will be calculated with a 95%CI.

Among others:

- Seroprevalence of SARS-CoV-2: number of children/ number of school staff in whom specific SARS-CoV-2 antibodies was detected by ELISA / total number of children/staff tested.
- SARS-CoV-2 seroconversion rate: Number of children/ number of school staff in whom presence of specific antibodies was detected by ELISA during any of the follow-up tests with a previous sample showing no specific antibody / total number of children/staff followed-up with a baseline negative serum sample, during the study period of 7 months.
- Cumulative incidence
- Incidence rates (using both the total population and the population excluding the non-susceptible from the prior sero-survey testing period)
- Proportion of asymptomatic cases
- Proportion of symptomatic episodes amongst positives versus negatives

A flow diagram of the participants will be created reflecting number of participants approached, eligible and included. The statistical analysis will account for the small differences in sampling probability due to the study design by using specialized procedures for complex (survey) sampling..

For the secondary objectives, uni- and multivariate analysis will be performed assessing risk, protective and predictive factors associated with sero-positivity among children and among staff. Relative risk of sero-positivity in function of specific risk factors (prior to analysis a directed acyclic graphs (DAG) will be constructed and risk factors will be analysed using Poisson regression and effect

measures will be re-calculated and presented as absolute risks and risk differences with their CI). Models will be assessed for presence of confounders and interaction.

When tables will be presented e.g. test positives versus test negatives at the end of the study, no p-values will be presented comparing differences in basic characteristics to avoid chance-findings.

A sensitivity analysis will be performed to estimate bias resulting from the imperfect accuracy of serology testing. If needed other sensitivity analysis will be performed and selection bias will be assessed. Depending on the amount of missing data imputation will be used.

Data analysis will be done by KUL (statistician) and Sciensano using statistical software already available to the analysis team (including STATA 14/ SAS/ R), while having the necessary licenses.

4. Expected outcome

Primary outcome: SARS-CoV-2 seroprevalence at each time point

Secondary outcomes:

- SARS-CoV-2 sero-incidence and seroprevalence over time
- Cumulative incidence
- Proportion of symptomatic sero-positive cases
- Participants characteristics associated with test-positivity

Findings will help to understand the dynamics of COVID-19 among children and support the implementation of preventive and other measures for this population group.

5. Quality assurance

The protocol will be reviewed by the different partners and published on Clinicaltrials.gov.

Questionnaire contents and tool will be piloted for understandability and to check if the tool functions well. Study nurses responsible for sample collection will be trained. Laboratory analysis will be performed at the Sciensano laboratories. A validation study of the oral swabs will be performed prior to the start of the study to assure the validity of the specimen sample among children. A data analysis plan will be available.

6. Potential Biases and limitations

Selection bias

- Due to feasibility choices. For example, participants ~~children~~ chosen will not be completely representative of the school-age children and school staff population of Belgium. This will be documented by comparing characteristics of the participants with census data and other data sources.
- Exclusion bias: Due to non-consent to the study. The non-consent rate will be calculated to estimate the importance of this bias.

Cluster bias (non-independence of events)

If the selected participants belong to the same group (same class, same school, same family, etc.), this can affect the risk of seroconversion. This effect will be minimized by the multiplicity of contact points investigated, correction of the sample size for the number of clusters and the exclusion of multiple children from the same household.

Information bias

- Misclassification
- Imperfect accuracy (and imperfect reference standard for corrections): sensitivity analysis can be performed correcting for imperfect accuracy of serological testing
- Precision - depending on prevalence

Confounding

- Unmeasured confounders.
- Confounders will be investigated using DAG's and adjusted for where justified.

7. Protection of human subjects and Ethical considerations

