PREVALENCE AND INCIDENCE OF ANTIBODIES AGAINST SARS-COV-2 IN CHILDREN AND SCHOOL STAFF MEASURED FOR ONE YEAR IN BELGIUM: A SERO-EPIDEMIOLOGICAL PROSPECTIVE COHORT STUDY – AMENDED PROTOCOL

July 2021

Summary

This protocol amendment describes changes in:

1. Main objective
2. Secondary objectives
3. Study population
4. Questionnaire
5. Testing periods of participants

The **table of changes**, with rationale, the amended protocol, the questions added to the questionnaire and informed consent forms are provided in the following pages. **The sections that have been changed are highlighted in yellow.**

Table of changes

Changes July 2021:

Change / addition	Rational	Affected protocol section

Testing periods: Extension of the study period from 1/9/2021 tot 31/3/2022 with addition of two testing periods (September 2021 and December 2021)
	
The pandemic has not been fully controlled and new waves remain possible. The evolution of the pandemic remains unclear, with the circulation of new variants of concern, a still ongoing vaccination campaign and, so far, no vaccine availability for the paediatric population. With the start of the new school year no vaccine will yet be licensed for use in the under 12 year olds, resulting in primary school children remaining a SARS-CoV-2 infection susceptible population while it is unclear how this will be impacted by a (partially) vaccinated adult population.
 
Further surveillance of the seroprevalence in the paediatric population will inform us on the proportion of children with prior infection. Vaccination in the adult population renders further follow-up of school staff less useful. Similarly, the higher likelihood of vaccination among secondary school pupils making further follow-up of this group also less useful.
 
Keeping the same primary school study population, which is selected to be representative for primary school children of 8-9 year old in Belgium, will enable us to continue providing Belgian paediatric estimates and having a one year cohort including the same children over time. This allows us to provide both seroprevalence point-prevalence estimates and follow changes in incidence. Additionally, we will be able to get more insight in waning immunity and how this is captured by diagnostic tools.
	
3. Methods 3.2. Study design 3.6. Data collection 3.6.1. Data collection procedure 7.6. Study insurance

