This study will make it possible to better describe the prevalence of circulating antibodies in children and school staff in Belgian primary and secondary schools as well as the incidence of new infections in this subpopulation since they will be followed for 7 months. Additionally, by also questioning household members in the case of the children and by questioning the school staff, we will gain a more in-depth insight in symptomatic COVID-19 disease within households in Belgium, by linking the results of the salivary antibody tests in symptomatic and asymptomatic children with disease information of household members. The study also aims to generate insights in the clinical presentation of the disease among school-aged children and school staff and to evaluate the effect of child behaviour (e.g. participation in outside school activities) on the infection rate among children.

The study will cover all regions¹ in Belgium (Brussels-Capital, Flemish and Walloon Region) and interim data from each wave can guide the Belgian policy makers and CELEVAL (Group of Belgian Experts in charge of COVID-19 related public measures) in their advice on specific COVID-19 related measures for school-age children in order to limit circulation of SARS-CoV-2 in Belgium and to prevent an overload of our healthcare system with a limited societal impact (e.g. school closures). This data might also guide the expert group who will give advice regarding vaccination strategies whether children should be included for vaccination to create herd immunity or not.

¹ A stratified selection of all of all municipalities.

2. Objectives

Main objective

To determine the prevalence and incidence of antibodies against SARS-CoV-2 in a sample of school-aged children and school staff (primary and secondary school) and primary school children only in Belgium at different time points.

Secondary objective

- Determine the cumulative incidence of SARS-CoV-2 from baseline to 7 months in the complete sample and 1 year among primary school children
- Determine the proportion of asymptomatic infections with SARS-CoV-2 in this sample
- Gain insight in the role of COVID-19 infection in household members of children and school staff in this sample
- Describe child characteristics and investigate potential risk factors for infection among school-age children
- Describe characteristics of school staff and investigate potential risk factors for infection among school staff

Exploratory objective

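### Infection outcomes have no vaccination rule, so vaccine-induced anti-S1 IgG would count as infection in staff at period 3 and in any vaccinated child at periods 4–5

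*Combined protocol and SAP*

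**What the plan says.** **Assay.** Section 3.6.3 describes an ELISA "measuring human antibodies of the class IgG targeting the recombinant S1 domain including the receptor binding domain". It adds: "Test results are qualitative and will be reported as presence versus absence of specific antibodies". No second antigen is planned.

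**Definitions.** Section 3.7 computes seroprevalence from participants "in whom specific SARS-CoV-2 antibodies was detected by ELISA / total number of children/staff tested". The seroconversion rate counts antibody detected "during any of the follow-up tests with a previous sample showing no specific antibody", divided by baseline-negative participants followed up over 7 months. Neither definition mentions vaccination. Cumulative incidence and the asymptomatic proportion are listed without a definition. Incidence rates have only their denominators specified; one version removes people already non-susceptible at the prior survey.

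**How results are read.** The secondary objectives in section 2 include "Determine the cumulative incidence of SARS-CoV-2 from baseline to 7 months in the complete sample", extended to one year for primary pupils, as well as asymptomatic infections and risk factors for infection. The July 2021 rationale says that the extended surveillance will show what share of children had been infected.

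**Vaccination.** The same rationale states: "Vaccination in the adult population renders further follow-up of school staff less useful". The last staff sample is period 3, April/May 2021 (section 3.2). Item b of the Appendices is headed "Additional questions to be added at questionnaire for parents at 4th and 5th testing period" and asks about the child's doses, dates and product and about vaccination of household adults. The July 2021 table of changes does not list section 3.7 as affected.

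**The concern.** The assay target is the spike S1 domain. A vaccine that raises anti-spike IgG gives the same positive result as an infection, and a qualitative reading cannot separate them. The documents do not state that the vaccines named in Appendix b do this, but the sponsor's reason for ending staff follow-up is consistent with it.

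Section 3.7 offers only ELISA positivity as a case criterion. An analyst who follows it would turn a vaccinated, previously negative staff member into a seroconverter, and then into an incident infection. If that person had no symptoms, the case would be counted as asymptomatic. Four results are exposed: staff cumulative incidence and incidence rates, the staff asymptomatic proportion, the staff risk-factor models, and the staff-versus-pupil comparison. The November 2020 table of changes gives that comparison as a reason for adding staff. Vaccine positives would raise the staff side only, because the July 2021 rationale says no vaccine had so far been available to children.

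**Working it through.** **1. The plan's own precision figures.** Margin = 1.96 × √(p(1−p)/n).
- Staff (section 3.4), p = 10%, effective n = 400: 1.96 × √(0.10 × 0.90/400) = 2.94 points; stated 3%.
- Children (section 3.3), p = 6%, effective n = 400: 1.96 × √(0.06 × 0.94/400) = 2.33 points; stated 2.3%.

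Both reproduce, and they serve as the yardstick below.

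**2. Bias formula.** Let p be the share truly infected, v the share vaccinated before the sample, and s the share of vaccinees positive on the saliva ELISA. Vaccination is taken as independent of infection and the test as otherwise perfect. Then the apparent share is p + (1−p)vs, and the bias is (1−p)vs. The documents give neither v nor s; both are assumptions.

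**3. Staff at period 3, if the positive share is read as the share ever infected.** With p = 10% (section 3.4) the bias is 0.90 × v × s:

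| v | s = 0.5 | s = 0.9 |
|---|---|---|
| 1% | 0.45 points | 0.81 points |
| 5% | 2.25 | 4.05 |
| 10% | 4.5 | 8.1 |
| 25% | 11.25 | 20.25 |
| 50% | 22.5 | 40.5 |

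The bias equals 3 points at v = 0.03/(0.90 × s): 3.7% for s = 0.9 and 6.7% for s = 0.5.

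**4. Staff seroconversion.** Of 820 staff, 10% positive at baseline leaves 738 at risk. With true conversion c, vaccine-only conversions add (1−c)vs. At v = 10% and s = 0.8:
- c = 5%: 0.95 × 0.10 × 0.80 = 7.6 points, or 738 × 0.076 = 56 people.
- c = 10%: 0.90 × 0.10 × 0.80 = 7.2 points, or 738 × 0.072 = 53 people.

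The simpler product 738 × 0.10 × 0.80 = 59 (8 points) counts vaccinees who were also infected, so it is slightly too high.

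At c = 5%, v = 10% and s = 0.5–0.9, apparent conversion is 5 + 4.75 = 9.8% to 5 + 8.55 = 13.6%. Vaccine-only cases then make up 4.75/9.75 = 49% to 8.55/13.55 = 63% of counted seroconverters.

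**5. Children at periods 4–5.** With p = 6% and v = 1%, the bias is 0.94 × 0.01 × (0.5 to 0.9) = 0.47–0.85 points, inside the 2.3-point margin. It reaches 2.3 points at v = 0.023/(0.94 × s), that is 2.7% (s = 0.9) to 4.9% (s = 0.5). The 7-month seroconversion definition does not reach these periods. The route is the one-year cumulative incidence and the reading of seroprevalence as past infection.

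**6. Whether Appendix b supports censoring at first dose.** Question 1.1 asks for the first-dose date only when one dose was given. Question 1.2 asks only for the second-dose date when two were given. For two-dose children the first-dose date is therefore not collected.

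**The case against.** The strongest reply is that the study measures antibodies. The primary outcome is seroprevalence, and a count of antibody carriers is correct whatever raised the antibodies. This stands: a reader might infer that the seroprevalence definition is itself wrong, and the documents do not support that.

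A reader might also infer that section 3.7 defines cumulative incidence and the asymptomatic proportion by ELISA. It does not define them at all. The accurate statement is that seroconversion is the only incidence-type outcome with a case rule, and nothing else is offered for the others.

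Nor do the documents show that staff vaccination went unrecorded. The staff questionnaire for periods 2 and 3 is listed but not reproduced. The July 2021 amendment came after staff period 3, so the absence of new staff questions there proves nothing.

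For children the risk was largely anticipated. The extension is confined to primary pupils, no licensed vaccine for under-12s was expected at the start of the school year, and vaccination status is asked. What is missing is a rule that uses the answers.

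Finally, section 5 promises a data analysis plan, and section 3.7 allows further sensitivity analyses, causal diagrams and checks for confounding. That plan may contain a rule, but none appears here. The named sensitivity analysis addresses assay accuracy. A vaccine antibody that is correctly detected is not an assay error, so a sensitivity/specificity correction would not remove it.

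**Conclusion.** The point holds for the infection outcomes, chiefly in staff at period 3. As section 3.7 stands, vaccine antibodies in a previously negative participant count as seroconversion, and no other criterion keeps them out of incidence, asymptomatic proportion or risk-factor results. The direction is upward for any positive coverage, given that vaccinees test positive; the size is unknown because the documents report no coverage. Under the assumptions shown, 4–7% staff coverage is enough to match the plan's 3-point margin, and each 10% vaccinated adds about 7.2–7.6 points to seroconversion. A larger inflation can be produced by assuming higher coverage, but that would restate the assumption and is not a finding.

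For children at periods 4–5 the effect is conditional on vaccination and probably small: under 1 point at 1% coverage. Treating the child estimates as compromised to the same degree as the staff estimates would go beyond the text.

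**What to change.** In section 3.7:
1. Report any-source seroprevalence (all ELISA positives) separately from the infection outcomes.
2. For seroconversion read as infection, cumulative incidence, incidence rates, asymptomatic proportion and risk factors, censor each participant at the first vaccine dose, with the last pre-dose sample as the last observation.
3. Staff: take vaccination dates from the period 3 questionnaire if they were recorded. If they are not available, end staff infection incidence at period 2 (February 2021) and label staff period 3 as any-source seroprevalence. This fallback assumes that few staff were vaccinated by February 2021, which the documents do not state.
4. Children: use the Appendix b answers and add a first-dose date for two-dose children. Without that field, censor at the last sample before the testing period at which vaccination is first reported.

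The cost is analysis wording and one date field, with no new sampling and no change in sample size. Fewer staff remain at risk in the last interval. Censoring may also be informative if vaccination is related to exposure, and this should be stated as a limitation. Other approaches are possible, such as excluding or separately reporting vaccinated participants, or testing stored samples for a non-vaccine antigen (section 7.5 allows further COVID-19 testing). Whichever is chosen should be written down before the staff period 3 infection outcomes are reported.
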